**7.1.3. Population of Interest**

The primary pharmacodynamic analyses will be based on the “All Subjects” population, unless otherwise specified.

**7.1.4. Statistical Analyses / Methods**

Details of the planned displays are provided in Appendix 10: List of Data Displays and will be based on GSK data standards and statistical principles.

Unless otherwise specified, endpoints / variables defined in Section 7.1.1 will be summarised using descriptive statistics, graphically presented (where appropriate) and listed.

**7.1.4.1. Statistical Methodology Specification**

Endpoint / Variables

 
Alterations in the previously identified immune cell mechanisms specifically related to neutrophil function as determined by changes in mRNA transcriptomics in induced sputum after 12, 28 and 84 days of treatment. The response variable will be mRNA intensities (logarithm base 2 scale).
 

Model Specification
The mRNA data gives results from ~14000 genes encoded by ~54000 probe sets. A subset of 638 probe sets specifically relating to the cell mechanisms of neutrophil function is specified in Section 13.6.5 This subset will comprise the primary statistical analysis dataset.

Each probe set will be analysed separately.

The log2 transformed mRNA intensities will be analysed in a repeated measures model under a Frequentist framework. The model will include a Treatment, Visit and Treatment\*Visit term. The Visit will consist of 4 levels: Screening (Baseline), Day 12, Day 28 and Day 84, and the Treatment will consist of three levels: Null (when Visit = Screening), All Placebo and All NEMI. An unstructured (UN) covariance structure will be fitted. The denominator degrees of freedom for use in significance testing will be computed using the Kenward Rogers approximation.

Back transformed baseline-adjusted ratios along with 95% CIs and two-sided unadjusted p-values will be calculated for each Visit for the All NEMI and All Placebo Treatments, i.e. Day 84, Day 28 and Day 12 in the All NEMI Treatment group vs Screening and Day 84, Day 28 and Day 12 in the All Placebo Treatment group vs Screening. Additionally, baseline adjusted ratios between All NEMI vs All Placebo will be calculated for Day 12, Day 28 and Day 84 along with 95% CI and two-sided unadjusted p-values, i.e. Day 84 in the All NEMI Treatment group vs Day 84 in the All Placebo Treatment group, similarly for Day 28 and Day 12. Other comparisons of interest may also be calculated such as means for each Visit and Treatment, i.e. Screening (Null Treatment), Day 12, 28 and 84 (All NEMI Treatment) Day 12, 28 and 84 (All Placebo Treatment).

To enable review by the study team, csv files will be created containing the output for all probe sets in scope for the primary statistical analysis will be generated sorted alphabetically by probe set ID. Separate csv files may be created containing only probe sets where the p-value for the comparisons is <0.05. Such probe sets will be ranked by fold change, with the expectation that, in general, a greater than a 1.5-fold change is scientifically meaningful. To comply with guidance regarding QC, csv files will be stored as a SAS dataset to ensure QC can be audited.

Following review by the study team of the results, a subset of probe sets may be identified and may be used for further reporting.

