## 2.2. Study Objective(s) and Endpoint(s)

Objectives	Endpoints
Primary Objectives	Primary Endpoints

 
To establish the PI3K<math>\delta</math>-dependent changes in previously identified immune cell mechanisms specifically related to neutrophil function using mRNA in sputum from patients with an exacerbation of COPD, with or without treatment with GSK2269557.
 
	
 
Alterations in previously identified immune cell mechanisms specifically related to neutrophil function as determined by changes in mRNA transcriptomics in induced sputum after 12, 28 and 84 days of treatment.
 

Secondary Objectives	Secondary Endpoints

 
To evaluate the effect of once daily repeat inhaled doses of GSK2269557 on lung parameters derived from HRCT scans in subjects with acute exacerbation of COPD, compared to placebo.
 
	
 
Change from baseline in siVaw, iVaw, iRaw, siRaw, total lung capacity, lung lobar volumes, trachea length and diameter at FRC and TLC after 12 days of treatment and after 28 days of treatment.
 

 
To assess the safety and tolerability of once daily repeat inhaled doses of GSK2269557 administered to subjects with acute exacerbation of COPD, compared to placebo.
 
	
 
Adverse events
 
Haematology, clinical chemistry
 
Vital signs
 
12-lead ECG
 

 
To evaluate the plasma PK of once daily repeat inhaled doses of GSK2269557 administered to subjects with acute exacerbation of COPD.
 
	
 
Day 1 plasma Cmax and trough (24 hours) post dose for inpatients.
 
Trough concentration after 12 days, 28 days, 56 days and 84 days of treatment.
 

 
To evaluate the effect of once daily repeat inhaled doses of GSK2269557 on lung function parameters in subjects with acute exacerbation of COPD compared to placebo.
 
	
 
To evaluate the effect of once daily repeat inhaled doses of GSK2269557 on lung function parameters in subjects with acute exacerbation of COPD compared to placebo.
 

Exploratory Objectives	Exploratory Endpoints

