#### NOTES:

- Sampling times: Screening, day 12, day 28 and day 84
- Inflammatory cytokine biomarkers are elevated in COPD patients. Expected to reduce with treatment.
- Microbiome biomarkers are drivers of exacerbations in COPD and are inhibited in preclinical disease studies
- PI3K $\delta$  transcriptome analysis in FTIH study has 16 genes identified (sputum) showing a consistent response with dose – all are down regulated.

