##### RNA transcriptome

- Affymetrix microarray mRNA data will be normalised using RMA in ARRAY STUDIO v8.0 or later by the Statistical Consultancy Group (SCG) within GSK. After normalisation, the data will be quality assessed and any samples deemed as QC fails will be excluded from any further analysis. This quality assessment will involve looking for outlying signals in both the normalised expression data and the MAS5 QC metrics generated from each sample. If any samples are excluded, the remaining data will be re-normalised. The output from the normalization will be log2 transformed mRNA intensity data.
- Summary mRNA data will be reviewed and a decision made on which probe sets are to be included in the SI dataset.
- Treatment ratios from the statistical analyses of mRNA intensity data will be converted to fold changes as follows:
  - If ratio  $\geq 1$  then fold change = ratio
  - If ratio  $< 1$  then fold change =  $-1/\text{ratio}$

The primary pharmacodynamic endpoint is based on a subset of probe sets defined as those that have previously identified immune cell mechanisms specifically related to neutrophil function.

The gene list that meets this criterion based on PII115119 D14 vs D1 gene changes, PII115117 and Metacore neutrophil pathways identified in PII115119 study. This gene list identified 258 genes in total after filtering for redundancy and was agreed by the study team is presented in [Table 3](#).

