**Table 3 Gene List that have previously identified immune cell mechanisms specifically related to neutrophil function**

Gene	Source	Gene	Source
CD177	PII115119 - Neutrophil migration	ITGAL	Metacore: IL8 Neutrophil migration
CXCR1	PII115119 - Neutrophil migration	ADAM17	Metacore: Inhibition of neutrophil migration
CXCR2	PII115119 - Neutrophil migration	C5	Metacore: Inhibition of neutrophil migration
FPR2	PII115119 - Neutrophil migration	C5AR1	Metacore: Inhibition of neutrophil migration
LTB4R	PII115119 - Neutrophil migration	CCR5	Metacore: Inhibition of neutrophil migration
PAK1	PII115119 - Neutrophil migration	CD34	Metacore: Inhibition of neutrophil migration
PXN	PII115119 - Neutrophil migration	CALM1	Metacore: Inhibition of neutrophil migration
PREX1	PII115119 - Neutrophil migration	CALM2	Metacore: Inhibition of neutrophil migration
TLN1	PII115119 - Neutrophil migration	CALM3	Metacore: Inhibition of neutrophil migration
SSH2	PII115119 - Neutrophil migration	FPR1	Metacore: Inhibition of neutrophil migration
F2RL1	PII115119 - Neutrophil infection response	ICAM2	Metacore: Inhibition of neutrophil migration
TLR10	PII115119 - Neutrophil infection response	IL1B	Metacore: Inhibition of neutrophil migration
CEACAM3	PII115119 - Neutrophil infection response	IL1R1	Metacore: Inhibition of neutrophil migration
TREML2	PII115119 - Neutrophil infection response	ITPR1	Metacore: Inhibition of neutrophil migration
DEFB124	PII115119 - Neutrophil infection response	ITPR2	Metacore: Inhibition of neutrophil migration
CLEC4C	PII115119 - Neutrophil infection response	ITPR3	Metacore: Inhibition of neutrophil migration
IFITM1	PII115119 - Neutrophil infection response	SELL	Metacore: Inhibition of neutrophil migration
CR1	PII115119 - Neutrophil infection response	MSN	Metacore: Inhibition of neutrophil migration
PMAIP1	FTIH - GSK'557 response	NFKB1	Metacore: Inhibition of neutrophil migration
S100P	FTIH - GSK'557 response	NFKB2	Metacore: Inhibition of neutrophil migration
PTGS2	FTIH - GSK'557 response	REL	Metacore: Inhibition of neutrophil migration
CCL20	FTIH - GSK'557 response	RELA	Metacore: Inhibition of neutrophil migration
EGR3	FTIH - GSK'557 response	RELB	Metacore: Inhibition of neutrophil migration
H1FO	FTIH - GSK'557 response	PECAM1	Metacore: Inhibition of neutrophil migration
NCOA3	FTIH - GSK'557 response	PRKCA	Metacore: Inhibition of neutrophil migration
TARP	FTIH - GSK'557 response	PRKCB	Metacore: Inhibition of neutrophil migration

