ICAM1	Metacore: IL8 Neutrophil migration	LRG1	Metacore: Transcription regulation of granulocytes
CXCL8	Metacore: IL8 Neutrophil migration	LTF	Metacore: Transcription regulation of granulocytes
ITGB2	Metacore: IL8 Neutrophil migration	ELANE	Metacore: Transcription regulation of granulocytes
LIMK1	Metacore: IL8 Neutrophil migration	LYZ	Metacore: Transcription regulation of granulocytes
MYLK	Metacore: IL8 Neutrophil migration	MXD1	Metacore: Transcription regulation of granulocytes

Gene	Source	Gene	Source
MYLK2	Metacore: IL8 Neutrophil migration	MAX	Metacore: Transcription regulation of granulocytes
MYLK3	Metacore: IL8 Neutrophil migration	PRTN3	Metacore: Transcription regulation of granulocytes
PPP1CB	Metacore: IL8 Neutrophil migration	MPO	Metacore: Transcription regulation of granulocytes
PPP1R12A	Metacore: IL8 Neutrophil migration	SPI1	Metacore: Transcription regulation of granulocytes
PDPK1	Metacore: IL8 Neutrophil migration	RARA	Metacore: Transcription regulation of granulocytes
PIK3CG	Metacore: IL8 Neutrophil migration	RXRA	Metacore: Transcription regulation of granulocytes
PIK3R5	Metacore: IL8 Neutrophil migration	SOCS3	Metacore: Transcription regulation of granulocytes
PIP5K1A	Metacore: IL8 Neutrophil migration	STAT3	Metacore: Transcription regulation of granulocytes
PIP5K1B	Metacore: IL8 Neutrophil migration	STAT5A	Metacore: Transcription regulation of granulocytes
PIP5K1C	Metacore: IL8 Neutrophil migration	STAT5B	Metacore: Transcription regulation of granulocytes
PRKCZ	Metacore: IL8 Neutrophil migration	FES	Metacore: Transcription regulation of granulocytes
PLD1	Metacore: IL8 Neutrophil migration	MYB	Metacore: Transcription regulation of granulocytes
PLPP6	Metacore: IL8 Neutrophil migration	MYC	Metacore: Transcription regulation of granulocytes
RAC1	Metacore: IL8 Neutrophil migration	CYBB	Metacore: Transcription regulation of granulocytes
RAC2	Metacore: IL8 Neutrophil migration	NCF1	Metacore: Transcription regulation of granulocytes
TLN2	Metacore: IL8 Neutrophil migration	NCF2	Metacore: Transcription regulation of granulocytes

Gene names converted to Affymetrix probe ID, resulted in 638 probes in total, these are presented in [Table 4](#).

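### The primary endpoint is about neutrophil mechanisms, but the plan reports 638 separate probe-set results and pre-specifies no statistic that summarises a mechanism or uses the recorded 16-gene directional prior

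*SAP*

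**What the plan says.** SAP section 2.2 words the primary endpoint at mechanism level: "Alterations in previously identified immune cell mechanisms specifically related to neutrophil function as determined by changes in mRNA transcriptomics in induced sputum". The time points are Days 12, 28 and 84.

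Section 13.6.5 builds the gene list: "This gene list identified 258 genes in total after filtering for redundancy". The list is then mapped to the array: "Gene names converted to Affymetrix probe ID, resulted in 638 probes in total". Section 7.1.4.1 sets the unit of analysis: "Each probe set will be analysed separately". Each model gives All NEMI against All Placebo at Days 12, 28 and 84, with 95% CIs and two-sided unadjusted p-values.

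The review files are "sorted alphabetically by probe set ID", and Table 6.1 in Appendix 10 uses the same sort. Section 7.1.4.1 also allows separate files limited to p<0.05 and ranked by fold change, with 1.5-fold as the scientific yardstick. The study team may then select a subset of probe sets for further reporting.

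The notes in section 13.6.5 record prior evidence on this drug: "transcriptome analysis in FTIH study has 16 genes identified (sputum) showing a consistent response with dose – all are down regulated". Table 3 marks those genes with the source label "FTIH - GSK'557 response" and groups the remaining genes under six other labels, all naming a neutrophil or granulocyte process.

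**The concern.** The endpoint asks whether mechanisms change, and the analysis reports whether individual probe sets change. Nothing pre-specified connects the two. Sections 2.4.1, 7.1, 7.2 and 9.1 and Table 6.1 contain no signature score, gene-set test, global test or count of directions. The plan holds both a grouping of the genes and, for 16 of them, an expected direction, but neither enters a model.

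The trial could therefore finish with a long list in which real and chance findings are mixed. Any statement about a mechanism would come from selection after the results are seen. The plan's recorded directional hypothesis, that the 16 genes fall together on drug, would never be tested as a whole.

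**Working it through.** **The plan's own figure.** Section 2.3 gives about 45 randomised, for about 15 + 15 subjects who provide sputum at every time point and complete. Carrying over the dropout of the initial plan (10 of 30), 30 / (1 − 1/3) = 45, so the figure reproduces. The SAP gives no SD, between-gene correlation or power for the primary endpoint. Those inputs below are assumptions.

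**Counts.** Table 3 carries the first-time-in-human label on 16 genes: PMAIP1, S100P, PTGS2, CCL20, EGR3, H1F0, NCOA3, TARP, CEACAM1, TTPAL, VPS37B, SYAP1, SPTBN1, EGR1, OSM and TBC1D22A. Their Table 4 probe sets, in that order, are 2+1+2+1+1+1+6+3+5+2+1+1+11+3+2+3 = 45. That is 16/258 = 6% of genes and 45/638 = 7% of probe sets.

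**Chance findings.** If nothing changes, the expected number with p<0.05 is 638 × 0.05 = 31.9 per nemiralisib-placebo comparison, or 3 × 31.9 = 95.7 over the three visits. These expectations do not depend on correlation between probe sets.

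**Power: one gene against a 16-gene mean.** Take a single visit, 15 per arm, two-sided 0.05 and the noncentral t with 28 df. Let d be the standardised effect in each gene and ρ the mean between-gene correlation. The SD of the mean score, relative to one gene, is √((1 + 15ρ)/16), so the score's standardised effect is d / √((1 + 15ρ)/16). If only half the genes respond, the numerator becomes d/2.

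For d = 0.6, one gene has power 0.35. For the score:

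| ρ | SD factor | Score effect | Power, all 16 respond | Power, half respond |
|---|---|---|---|---|
| 0.2 | 0.500 | 1.20 | 0.89 | 0.35 |
| 0.3 | 0.586 | 1.02 | 0.77 | 0.27 |
| 0.5 | 0.729 | 0.82 | 0.59 | 0.19 |
| 0.7 | 0.848 | 0.71 | 0.46 | 0.15 |

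For d = 0.5, one gene has 0.26, and the score has 0.75, 0.62 or 0.44 at ρ = 0.2, 0.3 or 0.5 when all 16 respond.

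**The same check at the plan's 1.5-fold yardstick.** log2(1.5) = 0.585. One probe set has power 87%, 54%, 34%, 24% or 18% if the SD is 0.5, 0.75, 1.0, 1.25 or 1.5 on the log2 scale. With Bonferroni over 638 the figures are 12%, 1.8%, 0.5%, 0.2% and 0.1%.

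**An average over the whole list would not help.** With SD 1.0 and ρ from 0.1 to 0.5, if only the 16 genes shift by 1.5-fold, a mean over all 258 genes has about 5% power or less. The score has to follow the Table 3 groups.

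**The case against.** The strongest reply is that probe-level analysis is a deliberate choice, stated consistently. Section 2.2 defines the mechanism endpoint through transcript changes, section 7.1.1 makes that operational as the 638-probe subset, and section 2.4.1 states the aim as estimation. There is no power claim or success rule to fail. This stands as far as it goes: the plan is not inconsistent in how it runs the models. It does not supply the missing step, because no rule says what pattern among 638 results would count as an altered mechanism.

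The output is also more than an alphabetical list, since the p<0.05 filter and fold-change ranking are available. That is correct. Those steps are optional, however, and they select individual probe sets after unblinding.

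A reader might infer that separate testing wastes most of the available power. The documents do not support that. SD, correlation and uniformity of effect are all assumed here. At ρ = 0.5 and d = 0.6, one gene keeps 0.35 of the score's 0.59. If the SD is about 0.5 log2, one probe set already has about 87% power at 1.5-fold. If only half the genes respond, the score does no better than one responding gene. Fifteen per arm is also the completer target. Earlier visits may have more subjects, and with 20 per arm one gene at d = 0.6 has 0.46.

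A reader might also infer that the 16-gene score alone would answer the primary question. It would not. Its Table 3 label is drug response, not a neutrophil process, and it covers 6% of the genes. Nor are these the only genes with a source in earlier study data. Section 13.6.5 also draws on gene changes in study PII115119, and Table 3 gives that study as the source of 18 genes, though the SAP states no direction for them.

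**Conclusion.** The concern holds in this form: the primary endpoint is stated for mechanisms, and no pre-specified statistic summarises a mechanism or uses the recorded all-down prior for the 16 genes. About 32 chance findings per nemiralisib-placebo comparison are expected alongside any real ones. This part does not depend on power; well-powered probe sets would still leave the step from list to mechanism undefined.

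The size of the power gain is conditional. It is large when correlation is low and all 16 genes respond, modest at correlation 0.7 (0.46 against 0.35), and absent when only half respond. The figures assume one visit, equal variances, a common correlation, 15 per arm and equal standardised effects among the responding genes. This is an analysis that should be added, and it leaves the planned models valid.

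**What to change.** Amend section 7.1.4.1 before unblinding:

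1. **Drug-response signature.** For each subject and visit, average the log2 intensities of the probe sets within each of the 16 first-time-in-human genes, standardise each gene, and average over genes. Averaging within gene first stops SPTBN1, with 11 of the 45 probe sets, from dominating. Analyse the score in the planned repeated-measures model and report the All NEMI minus All Placebo difference with 95% CI at Days 12, 28 and 84. State the expected direction as down, and describe it as a test of the prior drug-response signature.
2. **Mechanism-level summaries.** Calculate the same score for each Table 3 neutrophil and granulocyte source group, using the genes represented in Table 4. Analyse these two-sided, because the plan gives them no direction.
3. **Probe-level results.** Keep the 638-row table as descriptive.

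State the reference for standardisation in advance, for example the Screening mean and SD pooled over arms.

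The cost is seven extra model fits (one signature and six source groups) on data already planned, plus SAP wording. The downside should be stated in the plan: a mean score is diluted when only some genes respond, and it loses power where genes in a group move in opposite directions.

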**Table 1 Changes to Protocol Defined Analysis Plan**

Protocol	Reporting & Analysis Plan	
Statistical Analysis Plan	Statistical Analysis Plan	Rationale for Changes

 
Total lung capacity and lung lobar volumes included in HRCT secondary endpoint parameters
 
	
 
Total lung capacity and lung lobar volumes dropped from HRCT secondary endpoint parameters included as an exploratory endpoint parameter instead
 
	
 
The clinically relevant HRCT parameters are still to be decided. However, there was no clinical benefit seen in the comparison between GSK2269557 1000 mcg and Placebo in these parameters.
 

 
Analysis population:                             
 
All Subject All randomised subjects who receive at least one dose of the study treatment. This population will be based on the treatment the subject actually received.
 
Pharmacokinetic Subjects in the 'All subject' population for whom a pharmacokinetic sample was obtained and analysed.
 
 
 
	
 
Analysis population:                             
 
All Subject All randomised subjects who receive at least one dose of the study treatment. This population will be based on the treatment the subject actually received.
 
Pharmacokinetic Subjects in the 'All subject' population for whom a pharmacokinetic sample was obtained and analysed.
 
 
 
 
Note: The two subjects who were not compliant with inhaler instructions will be excluded from the outcome summaries if they received active treatment but will be included if they received placebo
	
 
2 subjects were not compliant with inhaler instructions and may not have received the full dose in amendment 4. Therefore, these subjects will be excluded from the outcome summaries if they received active treatment but will be included if they received placebo. Sensitivity analyses may be conducted including these subjects.
 

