### 2.3. Study Design

Overview of Study Design and Key Features	
Design Features	
 
• Multi-centre and Multi-Country
 
• Randomised
 
• Double-blind
 
• Placebo-controlled
 
• Parallel group
 

Dosing	
 
• Once daily, in the morning for 84 days
 
• Administered through the Diskus dry powder Inhaler
 

Time & Events	
 
• Refer to Appendix 2: Schedule of Activities
 

Treatment Assignment	
 
• Initially planned for approximately 30 subjects randomised to receive either 1000 µg GSK2269557 (Diskus) or matching Placebo in a 1:1 ratio as it was anticipated that 10 patients would drop-out. Twenty-eight subjects were randomised to this schedule, however, due to expiration date there was a protocol amendment following which additional subjects were subsequently randomised to receive either 700 µg GSK2269557 (Ellipta) or matching Placebo (Ellipta) in a 1:1 ratio. The protocol was updated such that approximately 45 subjects with an acute exacerbation of COPD would be randomized such that approximately 15 subjects on active and 15 subjects on placebo provide sputum at all the scheduled time points and complete the study.
 
• Subjects are assigned to treatment in accordance with the randomisation schedule generated by Clinical Statistics, using validated software.
 

Interim Analysis	
 
• No formal interim analysis will be conducted
 

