## 5. CONSIDERATIONS FOR DATA ANALYSES AND DATA HANDLING CONVENTIONS

### 5.1. Study Treatment & Sub-group Display Descriptors

Treatment Group Descriptions			
RandAll NG		Data Displays for Reporting	
Code	Description	Description	Order in TLF
	This will be derived as subjects who did not receive any treatment	No Treatment	1
	This will be derived as subjects in RandALL codes A or C	All Placebo	2
	This will be derived as subjects in RandALL codes B or D	All NEMI	3
A	Placebo	Placebo Diskus	4
B	GSK2269557 1000 mcg	NEMI Diskus	5
C	Placebo via Ellipta	Placebo Ellipta	6
D	GSK2269557 700 mcg	NEMI Ellipta	7

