#### NOTES:

- The following footnote will be presented on displays which use the "Placebo Diskus", "NEMI Diskus", "Placebo Ellipta" or "NEMI Ellipta" treatment groups:  
NEMI Diskus =1000 mcg Nemiralisib administered via the Diskus device; NEMI Ellipta =700 mcg Nemiralisib administered via the Ellipta device
- Order represents treatments being presented in TFL, as appropriate

Treatment groups "Placebo" and "Placebo via Ellipta" (RandAll NG codes A and C) will be combined into "All Placebo" treatment group. Similarly, treatment groups "GSK2269557 700 mcg" and "GSK2269557 1000 mcg" (RandAll NG codes B and D) will be combined into "All NEMI" treatment group.

Treatment comparisons will be displayed as follows using the descriptors as specified:

- All NEMI vs All Placebo

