### 5.3. Examination of Covariates and Subgroups

#### 5.3.1. Covariates and Other Strata

The list of covariates may be used in descriptive summaries and statistical analyses, some of which may also be used for subgroup analyses. Additional covariates of clinical interest may also be considered.

Category	Details
Covariates	Age, Sex, BMI, Country, Primary exacerbation severity

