### Model Checking & Diagnostics

- The Kenward and Roger method for approximating the denominator degrees of freedom and correcting for bias in the estimated variance-covariance of the fixed effects will be used.
- An unstructured covariance structure for the R matrix will be used by specifying 'type=UN' on the REPEATED line.
  - In the event that this model fails to converge, alternative correlation structures may be considered

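### The primary mRNA model pools two separately randomised device cohorts with no cohort term: a minor, cheap improvement, not a validity defect

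*SAP*

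**What the plan says.** Section 2.3 describes two randomisations in sequence. The first was 1:1 to 1000 µg by Diskus or placebo. It was then superseded: "Twenty-eight subjects were randomised to this schedule, however, due to expiration date there was a protocol amendment following which additional subjects were subsequently randomised", again 1:1, to 700 µg by Ellipta or matching placebo. The revised total is about 45, so that about 15 subjects per arm complete with sputum at every scheduled time point.

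Section 5.1 keeps four randomisation codes (A and B for Diskus, C and D for Ellipta) but builds the analysis groups across them. For All NEMI the entry reads "This will be derived as subjects in RandALL codes B or D"; All Placebo is built from A and C in the same way. The Amendment 4 entry in Section 1 calls the Ellipta dose comparable, which is the documented basis for pooling.

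The primary model in Section 7.1.4.1 contains Treatment, Visit and their interaction, and "the Treatment will consist of three levels: Null (when Visit = Screening), All Placebo and All NEMI". The only flexibility under its Model Checking & Diagnostics is "In the event that this model fails to converge, alternative correlation structures may be considered". Section 5.3.1 offers an optional list, "Age, Sex, BMI, Country, Primary exacerbation severity", and adds: "Additional covariates of clinical interest may also be considered". Device cohort is not on the list. By contrast, Sections 8.1.4.1 (FEV1, FVC) and 8.2.4.1 (HRCT) each say that additional covariates will be investigated.

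Table 1 in Section 2.1 records that "2 subjects were not compliant with inhaler instructions and may not have received the full dose in amendment 4". Those two are dropped from outcome summaries only if they were on active. Section 4.1 says their arm is not yet known, and the analysis that includes them is optional.

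**The concern.** Subjects were randomised within a cohort, but the primary analysis does not condition on cohort. A difference between the two recruitment periods that is common to both arms (calendar time, site mix, device) is left out of the mean model. It then sits in the residual of each of the 638 probe-set fits and widens every interval.

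If cohort shares also differ by arm, part of that difference enters the NEMI-to-placebo ratio. The active-only exclusion could contribute to such a difference, because both subjects belong to the Ellipta period. Probe sets are filtered at unadjusted p below 0.05 and ranked by fold change, with 1.5-fold as the mark of interest, so a small but systematic loss applies across the whole list.

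**Working it through.** **The plan's own figure.** The first plan allowed 10 dropouts in 30. Applying that rate to 30 completers gives 30/(1 − 10/30) = 45, as stated. The Ellipta cohort is then 45 − 28 = 17, so the Diskus share is f = 28/45 = 0.622 and f(1 − f) = 0.235.

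**Assumptions.** The SAP gives no cohort shift d, no SD s and no within-subject correlation r. I take d and s in log2 units, r from 0.3 to 0.7, complete data, and a shift already present at Screening and constant over visits.

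**Precision.** Put q = f(1 − f)d², V = s² + q and C = r·s² + q. With Screening modelled as a common-mean time point,

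SE ratio (term omitted / term fitted) = √[(V − C²/V) / (s²(1 − r²))].

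For s = 1, d = 1, r = 0.5: V = 1.235, C = 0.735, V − C²/V = 0.798, and √(0.798/0.75) = 1.031.

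| Shift | r | SE ratio |
|---|---|---|
| 0.5 SD | 0.5 | 1.009 |
| 1 SD | 0.5 | 1.031 |
| 1 SD | 0.3 | 1.050 |
| 1 SD | 0.7 | 1.017 |

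If the correlation instead decays by half at each visit step, to 0.125 between Screening and Day 84, the 1 SD figure at Day 84 is 1.071.

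**Gap in Diskus share, active minus placebo.**

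| Subjects excluded | Ellipta split (active:placebo) | Gap |
|---|---|---|
| None | 8:9 | 14/22 − 14/23 = 0.028 |
| One active | 9:8 | 14/22 − 14/22 = 0 |
| Both active | 9:8 | 14/21 − 14/22 = 0.030 |
| One active | 8:9 | 14/21 − 14/23 = 0.058 |
| Both active | 8:9 | 14/20 − 14/23 = 0.091 |

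**Shift of the ratio at the worst gap.** On the log2 scale, bias = d × gap × (1 − r)s²/(s² + q). Take d = log2(1.5) = 0.585 and f = 28/43 after two exclusions, so q = 0.078.

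- r = 0.5, s = 1: 0.585 × 0.091 × 0.5/1.078 = 0.025, a ratio of 1.017.
- r = 0.5, s = 0.5: 1.014.
- Range over r = 0.7 to 0.3: 1.009 to 1.024.
- Ceiling if the shift were absent at Screening: 1.5^0.091 = 1.038.

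**Cost of the term when there is no shift.** Compare 1/nA + 1/nP with 1/Σ(nA·nP/n), summed over cohorts.

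- Planned split, 14/8 v 14/9: √(0.08900/0.08893) = 1.0004.
- Both active excluded, 14/6 v 14/9: √(0.0943/0.0935) = 1.005.
- A chance-imbalanced completer set, 11/4 v 8/7: √(0.1393/0.1333) = 1.022.

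**The case against.** The strongest reply is that nothing here is wrong. Allocation is 1:1 in each period, so the pooled contrast is valid. No document reports a cohort shift, and Amendment 4 describes the dose as comparable. Section 7.1.1 specifies a balanced batch design for the laboratory work, and the Screening value with an unstructured covariance already absorbs much of a constant shift. All of this stands, and it is why the effect is small. However, dose comparability concerns the drug effect, not a shift common to both arms, and the batch design is not said to balance over cohort.

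A second reply is that the term is not free. That also stands. The 2.2% loss in an imbalanced completer set with no shift exceeds the 0.9% gain at 0.5 SD. Section 7.2.4 also carries the same model to about 54,000 probe sets in sputum and again in blood.

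A third is that the exclusion matters little. In part it does not: with nobody excluded, an odd 17 already gives a gap of 0.028, almost the same as both active at 9:8. Only the 8:9 split with active exclusions enlarges it.

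Three stronger readings are tempting and are not supported:

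- A reader might infer that treatment is confounded with period. It is not, because each period has its own concurrent placebo.
- A reader might infer that the primary model can never take a covariate. Section 5.3.1 is general and permissive, so what is missing is a provision in the primary section and the naming of cohort.
- A reader might assume a shift that appears only after Screening, which would give far larger standard-error inflation. The SAP offers no evidence of one.

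**Conclusion.** The point holds as a minor, inexpensive improvement to a stated model. The primary analysis ignores the groups within which subjects were randomised, and its own section leaves no route to include them. The price is about 1% to 3% in standard error for a cohort shift of 0.5 to 1 SD at correlation 0.5, up to 5% at correlation 0.3, and nothing if there is no shift. The ratio moves by about 1% to 2.4% only if three things coincide: both non-compliant subjects were on active, the Ellipta split was 8:9, and the cohorts differ by 1.5-fold.

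These sizes rest on an assumed shift present at Screening, complete data and the planned 28 + 17. The NEMI vs placebo contrast is valid with or without the term. The term does not show whether the two dose-and-device combinations have the same effect, and it does not cure the active-only exclusion, which needs its own answer.

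**What to change.** In Section 7.1.4.1, before unblinding:

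- Add device cohort (Diskus, Ellipta) and cohort-by-visit, including the Screening level, as fixed effects.
- Keep All NEMI vs All Placebo as the reported contrast.
- Compute all Screening and within-arm means with one common set of weights: the overall randomised cohort shares, the same for both arms and every visit (28/45 and 17/45 if enrolment is as planned). Arm-specific shares would put the imbalance back into the ratios versus Screening.
- If the model does not converge for a probe set, drop the cohort terms for that probe set and flag it in the output.

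In Section 5.3.1, name device cohort, to enter the FEV1/FVC and HRCT models as a main effect only. A full cohort-by-visit-by-region expansion of the untrimmed siVaw model would add 2 × 5 = 10 means. It is not asked for, since Section 8.2.4.1 already warns about sample size.

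The cost is SAP wording, a variable already coded in the randomisation, and four coefficients per probe set (one per visit), including the exploratory fits in Section 7.2.4. With no cohort shift the standard error rises by 0.04% at the planned split and by about 2% in a chance-imbalanced completer set.
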